Serum digoxin concentrations, BUN, Creatinine, CBC, Electrolytes (Na, K) and ECGs will be obtained weekly. pregnancy testing for female participants of childbearing potential and a baseline screening to determine if you are eligible for this study. Peripheral blood (25ml) in EDTA tubes (purple top) will be obtained at 0, 1, 2, 3 weeks after starting digoxin, with written consent and in accordance with the guidelines of Yale University ethics committee. PMN and monocytes will be isolated using PolymorphPrep (Axis-Shield) according to standard procedure, and purity will be determined by flowcytometric analysis. Spontaneous ROS of PMNs will be measured by culturing neutrophils with CM-H2DCFDA for 30 minutes, washing, followed by kinetic analysis of intracellular ROS with fluorescent plate reader. Neutrophils up-regulate ROS spontaneously in culture, and for each sample the untreated aliquot will be the control for the digoxin treated aliquot. Monocytes will be stimulated LPS (100ng/ml) for 3 hrs after which cDNA will be prepared and qPCR conducted for IL-1B, TNF- α and IL-6. cDNA and supernatant will be stored for further analysis based on initial results.

These initial numbers are based the use of similar assays in the preliminary data. We will obtain additional assistance from [name] Professor of Biostatistics at the University of Massachusetts, who will 1) review of study design, including sample size and specimen utilization; 2) develop an appropriate data management system to provide data capture and edit capabilities; 3) develop appropriate statistical analysis, quality assurance, and quality control plans; 4) conduct the statistical analysis and provide material for presentation/publication; and 5) provide resources to assure reproducible research. Please see letter of support.

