F) Pregnancy: *The chance of a female subject to become pregnant on a 4-week study is very less, if in case this does happen they will be asked to stop the drug and withdraw from the study immediately. We do not intend to follow the pregnancy and birth outcome.*

Drug preparation: Digoxin is commercially available as a 0.05mg/ml elixir (Boehringer Ingelheim). The appropriate dosing of digoxin and control will be prepared with the help of the Yale Center for Clinical Investigation (YCCI) as detailed in the facilities and resources. Stopping criteria: Subjects will be removed from the study if any serum digoxin level is above 0.8ng/ml, or if there are any abnormalities in blood tests or ECGs. Data from these subjects will not be used in the analysis. Analysis, expected outcome and alternative approaches: It is expected that there will not be a significant difference in the neutrophil ROS and monocyte qPCR results in control group A between the four time points. It is expected that for group B and C, both neutrophil ROS and monocyte qPCR levels will be lower at time points 1, 2, 3 weeks as compared to time 0, and as compared to all time points of group A. It is not clear if in group D time points of week 1, 2, and 3 will be any different from time point 0. For the time points where significant differences are found we will perform additional luminex assay with the supernatant using the luminex five plex panel (GM-CSF, IL-1B, IL-6, IL-8, TNF- α). There will also be an analysis of the production of ROS and qPCR levels in relation to serum digoxin levels at the time that the analysis samples were obtained. The combinations of these analysis will establish that digoxin taken orally is effective in reducing inflammatory responses, and will also provide information on dose response for oral dosing as well as serum concentrations.

5. Genetic Testing N/A

A. Describe

- i. the types of future research to be conducted using the materials, specifying if immortalization of cell lines, whole exome or genome sequencing, genome wide association studies, or animal studies are planned *Write here*
- ii. the plan for the collection of material or the conditions under which material will be received *Write here*
- iii. the types of information about the donor/individual contributors that will be entered into a database *Write here*
- iv. the methods to uphold confidentiality *Write here*

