- Risks and Inconveniences of an electro-cardiogram (EKG): EKG is very safe procedure which is being performed very commonly for evaluation of cardiac status. There is no risk of performing EKG to the subjects, however, there may be slight inconvenience of cold sensations to the skin related to the application of gel at the site of EKG leads placement.

11. **Minimizing Risks:** Describe the manner in which the above-mentioned risks will be minimized.

1. Each participant will be enrolled only after signing an informed consent in the presence of a study coordinator. Participants will have adequate opportunity to review the informed consent and to ask any questions they may have about the research protocol, compensation, risks, and benefits of taking part in the study.
2. Blood draws and other biological sample collections will be performed by trained personnel. pregnancy testing for female participants of childbearing potential and a baseline screening to determine if you are eligible for this study.
3. A written detailed collection procedure is provided to minimize spilling during collection.
4. Serum digoxin concentrations, BUN, Creatinine, CBC and ECGs will be obtained weekly to monitor the adverse effect of digoxin. In case, subject is having adverse effect related to digoxin, they will be removed from study and medical care will be provided at Yale new haven hospital if needed.
5. In terms of potential drug allergies, all subjects will be asked standardized questions about previous allergic reactions to digoxin. If a participant reports a digoxin allergy, they will be excluded. We will contact (telephone, email, or text message) each participant within three days of starting the oral digoxin in order to assess tolerability.

6. There may be low risk of breach of confidentiality, however we will follow appropriate data safety plan to minimize the breach of confidentiality. In addition, unauthorized personnel will not be allowed to have access to subject's confidential information.

7. If study subjects express a desire to discontinue the protocol, for any reason, the intervention will be immediately terminated and consent to participate may be rescinded at the subject's discretion.

12. Data and Safety Monitoring Plan: Include an appropriate Data and Safety Monitoring Plan (DSMP) based on the investigator's risk assessment stated below. (Note: the HIC will make the final determination of the risk to subjects.)

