- a. What is the investigator's assessment of the overall risk level for subjects participating in this study? *Risks are minimal.*
- b. If children are involved, what is the investigator's assessment of the overall risk level for the children participating in this study? *Write here*
- c. Include an appropriate Data and Safety Monitoring Plan. Examples of DSMPs are available here <http://your.yale.edu/policies-procedures/forms/420-fr-01-data-and-safety-monitoring-plans-templates> for
 - i. Minimal risk
 - ii. Greater than minimal

Greater Than Minimal Risk DSMP

1. Personnel responsible for the safety review and its frequency:

The principal investigator will be responsible for monitoring the data, assuring protocol compliance, and conducting the safety reviews at the specified frequency, which must be conducted at a minimum of every 6 months (including when reapproval of the protocol is sought). During the review process, the principal investigator (monitor) will evaluate whether the study should continue unchanged, require modification/amendment, or close to enrollment. Either the principal investigator, the IRB have the authority to stop or suspend the study or require modifications.

2. The risks associated with the current study are deemed greater than minimal for the following reasons: (choose those that apply)

1. We do not view the risks associated with the _____ as minimal risks.
2. We do not view the risks associated with the combined use of _____ and _____ as minimal risks.
3. Given the now established safety and validity of the current drug _____ in our prior work, we do not view the proposed studies as high risk.
4. Given our experience with the combined co-administration _____, we do not view the proposed studies as high risk.

Although we have assessed the proposed study as one of greater than minimal risk, the potential exists for anticipated and/or unanticipated adverse events, serious or otherwise, to occur since it is not possible to predict with certainty the absolute risk in any given individual or in advance of first-hand

experience with the proposed study methods. Therefore, we provide a plan for monitoring the data and safety of the proposed study as follows:

3. Attribution of Adverse Events:

Adverse events will be monitored for each subject participating in the study and attributed to the study procedures / design by the principal investigator (*[name]*) according to the following categories:

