Adherence analysis will be ascertained using pill counts for each participant at the weekly visits. For safety analyses, we will record any adverse events, both serious (SAE) and not, described by the participant at each weekly visit. Each AE will include a description of the AE/SAE, relatedness to digoxin, and resolution. These will be summarized by treatment group and, if there are three or more participants in any one group with a specific AE/SAE, we will conduct a statistical test (Likelihood Ratio Chi-Square) to determine any statistically significant difference among the treatment groups using the analogous approach as above to first test for any difference in the incidence of AE/SAE among the three treatment groups followed by conducting the three pairwise comparisons, again using the Likelihood Ratio Chi-Square. Because this is a safety analysis, the critical p-value is left at 0.05 for all comparisons to avoid increasing the probability of a Type II error.

SECTION II: RESEARCH INVOLVING DRUGS, BIOLOGICS, RADIOTRACERS, PLACEBOS AND DEVICES

If this section (or one of its parts, A or B) is not applicable, check off N/A and delete the rest of the section.

A. RADIOTRACERS

N/A

1. Name of the radiotracer: *Write here*
2. Is the radiotracer FDA approved? YES NO

If NO, an FDA issued IND is required for the investigational use unless RDRC assumes oversight.

3. Check one: IND# *Write here* or RDRC oversight (RDRC approval will be required prior to use)
4. **Background Information:** Provide a description of previous human use, known risks, and data addressing dosage(s), interval(s), route(s) of administration, and any other factors that might influence risks. If this is the first time this radiotracer is being administered to humans, include relevant data on animal models.
Write here
4. **Source:** Identify the source of the radiotracer to be used. *Write here*
5. **Storage, Preparation and Use:** Describe the method of storage, preparation, stability information, method of sterilization and method of testing sterility and pyrogenicity.
Write here

B. DRUGS/BIOLOGICS

N/A

1. If an **exemption from IND filing requirements** is sought for a clinical investigation of a drug product that is lawfully marketed in the United States, review the following categories and complete the category that applies (and delete the inapplicable categories):

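### Safety findings without symptoms, and the removals they trigger, are not tabulated by arm in the plan as worded

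*Combined protocol and SAP*

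**What the plan says.** Four places in Section I bear on this.

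- **Item 13, Statistical Considerations (safety analyses).** The events to be used are given as "we will record any adverse events, both serious (SAE) and not, described by the participant at each weekly visit". The plan continues: "These will be summarized by treatment group". A Likelihood Ratio Chi-Square follows when at least three participants in one group have the same specific event.
- **Item 4, Research Plan.** "Serum digoxin concentrations, BUN, Creatinine, CBC, Electrolytes (Na, K) and ECGs will be obtained weekly". Under the stopping criteria, subjects are to be "removed from the study if any serum digoxin level is above 0.8ng/ml, or if there are any abnormalities in blood tests or ECGs". The next sentence reads: "Data from these subjects will not be used in the analysis".
- **Item 11, Minimizing Risks, point 4.** The purpose of the tests is stated: "Serum digoxin concentrations, BUN, Creatinine, CBC and ECGs will be obtained weekly to monitor the adverse effect of digoxin". It adds: "In case, subject is having adverse effect related to digoxin, they will be removed from study".
- **Item 12, Data and Safety Monitoring Plan, point 3.** "Adverse events will be monitored for each subject participating in the study". The investigator attributes and grades events, and reviews them after each subject completes. No comparison by arm is mentioned.

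**The concern.** A raised digoxin level, a potassium shift or an ECG change without symptoms is not something a participant can describe. Yet these are the trial's main objective safety data. They are collected every week to detect harm from digoxin, and any one of them ends participation. The planned safety summary by arm is worded around a different source of information, and no section plans a count by arm of abnormal tests, levels above the limit, or removals.

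The data exclusion in the stopping criteria makes this worse or leaves it unchanged, depending on its scope, which is not stated. At stake is a report in which one dose group loses several subjects to the trial's own stopping rule and still shows no safety events.

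**Working it through.** The plan states no figure to reproduce here. The check is mainly of the text, followed by an illustration with assumed counts.

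**Step 1: where could each kind of finding be reported by arm?**

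| Finding | Safety summary (item 13) | Mixed models of biochemical measures (item 13) | Analysis against serum level (item 4) |
|---|---|---|---|
| Symptom the participant describes | Yes | No | No |
| Abnormal BUN, creatinine, Na, K, CBC | Not as worded | Possibly mean levels of some; not counts of abnormalities | No |
| Abnormal ECG | Not as worded | No | No |
| Digoxin level above 0.8 ng/ml | Not as worded | Not as a count | Level used only in relation to ROS and qPCR |
| Removal under the stopping rule | Not as worded | No | No |

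The term for the mixed-model outcomes is undefined. Item 4 describes its expected results as neutrophil ROS and monocyte qPCR, so those assays are the natural reading. The wider reading still leaves ECGs, counts of abnormalities and removals uncovered.

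**Step 2: scope of the exclusion.**

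- If it covers only ROS and qPCR, as the sentence after it suggests, removed subjects' described symptoms stay in the safety summary. The test findings that removed them still have no place there.
- If it covers safety too, the described symptoms are lost as well, and the denominator shrinks.

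**Step 3: illustration.** Inputs: 15 per arm (item 4). Assumed: 3 subjects on 3 mcg/kg/day are removed for a finding without symptoms, and nobody in that arm describes an event. The documents give no event rate.

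Exact (Clopper-Pearson) 95% limits for x of n: the lower limit solves P(X ≥ x) = 0.025 and the upper solves P(X ≤ x) = 0.025. For x = 0 the upper limit is 1 − 0.025^(1/n).

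- Complete table: 3/15 = 20%, CI 4.3% to 48.1%.
- As worded, exclusion limited to efficacy: 0/15, upper limit 1 − 0.025^(1/15) = 21.8%.
- As worded, exclusion covering safety: 0/12, upper limit 1 − 0.025^(1/12) = 26.5%.

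**Step 4: how likely is at least one such finding in an arm?** With assumed true rate p, the expected number is 15p and P(at least one) = 1 − (1 − p)^15.

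| Assumed p | Expected among 15 | P(at least one) |
|---|---|---|
| 5% | 0.75 | 0.537 |
| 10% | 1.5 | 0.794 |
| 20% | 3 | 0.965 |

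**The case against.** The strongest reply is that the safety clause is loosely worded and not a deliberate filter. It speaks of any adverse events. Item 11 ties the weekly tests to adverse effects of digoxin, and item 12 has the investigator monitor and review all adverse events. An investigator could log an abnormal ECG or potassium as an adverse event, and it would then reach the summary. This is possible, but the plan does not say that test findings without symptoms are recorded as adverse events, and the literal wording points the other way.

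Second, little is lost for good. Item 4 provides for laboratory upload to the study database with range checks, and a biostatistician is to develop analysis plans. That is correct, and it is why the fix is cheap. It makes the data available without planning the table, and no section defers safety tables to later work.

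Third, the mixed models may already compare some labs by dose and week. This stands in part. A reader might infer that no laboratory value is compared between arms at all, and the undefined term does not allow that to be said.

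Three other stronger readings are tempting and not supported:

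- *That a significant safety difference would be hidden.* For 3/15, 0/15 and 0/15 the plan's test gives 2·[3 ln 3 + 12 ln(12/14) + 30 ln(15/14)] = 7.03 on 2 df, p = 0.030. The plan tests only a specific event, so this requires all three subjects to share one finding. The exact probability for the same table is 3·C(15,3)/C(45,3) = 0.096.
- *That counting levels above 0.8 ng/ml would test the statement in Section II, B.2 that digoxin has no side-effects within or below the therapeutic range.* The documents do not say where 0.8 ng/ml lies in that range, so the count describes the stopping trigger only.
- *That these findings would go unseen.* The investigator, and through the investigator the IRB, may well see them. What is missing is the view by arm.

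**Conclusion.** The point holds in a limited form. As worded, the plan does not tabulate by arm the symptom-free findings that end participation, or the removals themselves, and it does not say whether removed subjects' data stay in the safety analysis. In the illustration an observed 20% is reported as 0%, with the denominator at 15 or 12.

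This rests on a literal reading of the clause about events the participant describes, and on no section elsewhere planning such a table; none was found. The counts and rates are assumed. What is lost is a description of tolerability by dose, not a firm test result, and the monitoring of individual subjects is unaffected. It should be corrected before the data are analysed.

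**What to change.** 1. In item 4, stopping criteria: state that the data exclusion does not apply to safety analyses.
2. In item 13: define the safety set as all subjects who took at least one dose, by assigned arm, whether or not they were later removed.
3. In item 13: add one descriptive table by arm, with counts and exact 95% confidence intervals and no significance tests. Its rows are abnormal labs, abnormal ECGs, removals by trigger, and digoxin level above 0.8 ng/ml. The last row is informative mainly within the two active arms, as a count of the stopping trigger.
4. Keep the Likelihood Ratio Chi-Square for reported AEs and SAEs only, so that the new rows do not fall under the testing rule.

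The cost is wording in two items and a little more analysis work. No new visits or procedures are needed, since the tests are already done weekly. The table will not settle whether the arms differ: at 15 per arm, even 0/15 is compatible with a true rate of up to 21.8%.

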
regulate expression of numerous genes. Interestingly, digoxin does not alter PKM2 kinase activity but suppresses PKM2 dependent transcriptional activity. This area is significant because sterile inflammation (SI) is the central pathological process in AH. Our results identify PKM2 as a key molecule in liver sterile inflammation which can be therapeutically targeted. The identification of digoxin as a PKM2 binder, which leads to critical anti-inflammatory effects, provides a novel opportunity to reduce liver inflammation in AH. We have further identified a unique molecular profile from a pilot aptamer-proteomic screen which will be expanded to the whole InTeam cohort to provide predictive markers for severe AH.

4. **Research Plan:** Summarize the study design and research procedures using non-technical language that can be readily understood by someone outside the discipline. **Be sure to distinguish between standard of care vs. research procedures when applicable, and include any flowcharts of visits specifying their individual times and lengths.** Describe the setting in which the research will take place.

Test if administering digoxin orally to healthy subjects results in a reduction in innate immune inflammatory responses in the peripheral blood.

We need to obtain peripheral blood lymphocytes from healthy subjects on different doses of digoxin to test if digoxin has an effect on the immune response of PBLs.

A) There will be three study groups.

Groups:

A: Placebo n=15

B: Digoxin 3 mcg/Kg/day n=15

C: Digoxin 0.15 mcg/Kg/day n=15

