- B. What are the conditions or procedures for sharing of materials and/or distributing for future research projects? *Write here*
- C. Is widespread sharing of materials planned? *Write here*
- D. When and under what conditions will materials be stripped of all identifiers? *Write here*
- E. Can donor-subjects withdraw their materials at any time, and/or withdraw the identifiers that connect them to their materials? *Write here*
 - i. How will requests to withdraw materials be handled (e.g., material no longer identified: that is, anonymized) or material destroyed? *Write here*
- F. Describe the provisions for protection of participant privacy *Write here*
- G. Describe the methods for the security of storage and sharing of materials *Write here*

6. **Subject Population:** Provide a detailed description of the types of human subjects who will be recruited into this study.
In total 60 healthy subjects ≥18 years and ≤70 years with no known clinical history will be recruited for this study.

7. **Subject classification:** Check off all classifications of subjects that will be specifically recruited for enrollment in the research project. Will subjects who may require additional safeguards or other considerations be enrolled in the study? If so, identify the population of subjects requiring special safeguards and provide a justification for their involvement.

 Children	 Healthy	 Fetal material, placenta, or dead fetus
 Non-English Speaking	 Prisoners	 Economically disadvantaged persons
 Decisionally Impaired	 Employees	 Pregnant women and/or fetuses
 Yale Students	 Females of childbearing potential	

NOTE: Is this research proposal designed to enroll children who are wards of the state as potential subjects?
 Yes No

8. **Inclusion/Exclusion Criteria:** What are the criteria used to determine subject inclusion or exclusion?

Inclusion Criteria

1. *Age >18 y ≤ 70 years*
2. *subjects with normal serum creatinine, normal EKG and currently not taking any medication.*

Exclusion criteria

1. *Autoimmune liver disease (ANA > 1/320)*
2. *Chronic viral hepatitis*
3. *Hepatocellular carcinoma*
4. *Complete portal vein thrombosis*
5. *Extrahepatic terminal disease*
6. *Pregnancy*

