7. *Treatment with prednisolone or pentoxifyllin for more than 3 days prior to inclusion/start date*

8. Active alcohol abuse (>50 g/day for men and >40 g/day for women) in the last 3 months
9. AST > ALT and total bilirubin > 3 mg/dl in the past 3 months
10. Liver biopsy and/or clinical picture consistent with alcoholic hepatitis
11. Lack of signed informed consent.
12. Known hypersensitivity to digoxin or other forms of digitalis, ventricular fibrillation.
13. Any significant medical conditions, any electrolyte abnormalities, over the counter medications, natural products and prescription drugs.
14. Breastfeeding mothers.

9. How will **eligibility** be determined, and by whom? Write here

The eligibility will be determined by PI and his team according to their IRB protocol.

10. **Risks:** Describe the reasonably foreseeable risks, including risks to subject privacy, discomforts, or inconveniences associated with subjects participating in the research.

The following risks are associated with participating in the study:

- Adverse effects from digoxin and its toxicity. Symptoms of digoxin toxicity include: confusion, irregular pulse, loss of appetite, nausea, vomiting, diarrhea, fast heartbeat, vision changes (which could be unusual, but includes blind spots, blurred vision, changes in how colors look, and seeing spots), decreased consciousness, decreased urine output, difficulty breathing when lying down, excessive nighttime urination, and overall swelling
- Allergic reaction to digoxin (nausea, vomiting, diarrhea, loss of appetite, weakness, dizziness, headache, anxiety, depression, slow heart rate, enlarged or tender breasts in men, or skin rash).
- Risks and discomforts of phlebotomy: To obtain detailed biochemical liver function tests and blood samples for research, blood sampling will be required. Patients will have 4 venipunctures during the period of evaluation (28 days). Each venipuncture will remove ~18 ml of blood. However, no more than 6 ml/kg will be drawn from any one person during this 4-week period. Blood collection by venipuncture is associated with mild discomfort, and possible risk of localized bruising, phlebitis, or extravasation. The risk of infection or fainting is extremely small.

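### Adverse events are tested only term by term, with no participant-level comparison of any toxicity symptom, so toxicity scattered at about one symptom per person would usually go untested

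*Combined protocol and SAP*

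**What the plan says.** Section I, item 13 (Statistical Considerations) has adverse events recorded at each weekly visit and summarised by treatment group. Testing is conditional: "if there are three or more participants in any one group with a specific AE/SAE, we will conduct a statistical test". The test is a likelihood-ratio chi-square. Its first step is an overall test, "to first test for any difference in the incidence of AE/SAE among the three treatment groups". As a second step the groups are taken two at a time with the same statistic: "followed by conducting the three pairwise comparisons, again using the Likelihood Ratio Chi-Square". On error control, "the critical p-value is left at 0.05 for all comparisons"; the stated reason is to avoid raising the Type II error.

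Item 10 (Risks) gives the toxicity picture: "Symptoms of digoxin toxicity include: confusion, irregular pulse, loss of appetite, nausea, vomiting, diarrhea, fast heartbeat, vision changes", followed by five more symptoms. With vision changes counted once, that makes 8 + 5 = 13.

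Item 4 (Research Plan) sets 15 per group, with placebo as group A, "B: Digoxin 3 mcg/Kg/day n=15" and "C: Digoxin 0.15 mcg/Kg/day n=15". Item 6 instead gives "In total 60 healthy subjects", which would be 60/3 = 20 per group.

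The plan defines no coding dictionary, no grouping of terms, and no comparison of participants with any event or any toxicity symptom.

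**The concern.** Thirteen different complaints can all reflect one drug effect, yet the plan counts each complaint separately. Six of 15 participants in a digoxin group could each report a different listed symptom, with none in the other groups, and no test would be run.

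The wording about incidence of AE/SAE could be read as overall incidence. Even on that reading, any test still waits for three people in one group to share a term.

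At stake is whether the trial has any pre-specified between-group statement about toxicity in healthy volunteers who get no direct benefit. The plan leaves safety tests at 0.05 to protect against missed signals, and its unit of comparison works against that aim.

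**Working it through.** **Plan's own figure.** There is none to reproduce: the documents give no adverse event rate, no power for safety and no derivation of the threshold of three. The 0.05/3 = 0.017 in item 13 applies to the biochemical measures.

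**Inputs from the documents.** 15 per group; 13 symptoms; trigger of three in one group with the same term; likelihood-ratio chi-square at 0.05. **Assumed:** rates of affected participants, number of symptoms each, and symptoms equally likely unless stated.

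**Step 1: the plan's statistic on fixed tables.** G² = 2 Σ O ln(O/E). With three groups there are 2 df, so p = exp(−G²/2).

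- 6/0/0 participants with any symptom (E = 2 affected and 13 unaffected per group): G² = 2[6 ln(6/2) + 9 ln(9/13) + 30 ln(15/13)] = 2[6.592 − 3.310 + 4.293] = 15.15, p = 0.0005. Under the plan this table is not tested if the six symptoms differ.
- 6/1/1: G² = 7.23, p = 0.027. 6/2/2: G² = 3.92, p = 0.14.
- 3/0/0 on one term: G² = 7.03, p = 0.030.
- 2/0/0 on one term: G² = 4.58, p = 0.101. This is the smallest three-group p-value possible with at most two per group.

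So the threshold of three discards no by-term result that could have been significant. What is missing is the pooled comparison.

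**Step 2: chance that the trigger is met, one symptom each.** With k affected in a group, P(k) = 1 − k!·[x^k](1 + x + x²/2)^13 / 13^k.

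| k of 15 affected | 3 | 4 | 5 | 6 | 8 | 10 | 11 |
|---|---|---|---|---|---|---|---|
| P(trigger) | 0.6% | 2.2% | 5.3% | 9.9% | 24% | 43% | 53% |

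Averaging P(k) over a binomial number affected gives 12.6% for a group with a 40% rate and 0.25% for a group with a 10% rate. For the whole trial: 1 − (1 − 0.126)(1 − 0.0025)² = 13%.

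**Step 3: detection at 0.05, 15 per group.** By-term figures are simulated. Pooled figures are enumerated exactly with the same likelihood-ratio test. Rates are for one digoxin group and then the other two groups.

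| Assumed rates | Symptoms each | Trigger met | By-term test significant | Pooled test significant |
|---|---|---|---|---|
| 40/10/10 | 1 | 13% | 10% | 57% |
| 40/10/10 | 2 | 55% | 42% | 57% |
| 40/10/10 | 3 | 82% | 65% | 57% |
| 40/0/0 | 1 | 13% | 13% | 97% |
| 40/0/0 | 2 | 53% | 53% | 97% |
| 40/0/0 | 3 | 80% | 80% | 97% |
| 40/20/20 | 1 | 16% | 10% | 23% |
| 40/20/20 | 2 | 63% | 36% | 23% |
| 40/20/20 | 3 | 89% | 57% | 23% |
| 20/20/20 (no effect) | 1 | 6% | 4% | 8% |
| 20/20/20 (no effect) | 2 | 31% | 16% | 8% |
| 20/20/20 (no effect) | 3 | 61% | 29% | 8% |

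**Sensitivity.** With 70% of the weight on the four gastrointestinal symptoms, 40/10/10 and one symptom each, the trigger is met in 32% of trials and the plan detects a difference in 23%. At 20 per group (the 60-subject figure), 40/10/10 and one symptom each gives trigger 28%, by-term 21%, pooled 68%.

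**Exact test on the pooled endpoint.** It detects 47% at 40/10/10, and gives 3% false positives at 20/20/20 where the likelihood-ratio test gives 8%.

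**The case against.** The strongest case against rests on the single-symptom assumption. A reader might infer that digoxin toxicity would usually go untested whatever its pattern. The documents do not support that, because they do not say how many symptoms an affected person would report. With two or three each, the trigger is met in 55% or 82% of trials at 40/10/10. Item 11 removes subjects who have a digoxin-related adverse effect. That may hold down the number of symptoms per person, but this is a possibility and not a figure.

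The pooled endpoint is also not uniformly better. At three symptoms each with 10% background, or at two or three each with 20% background, the by-term tests flag more often. Part of that is uncorrected multiplicity, as the no-effect rows show, but the plan accepts this openly. This part of the objection stands, and it is why the pooled comparison should be added to the by-term tests and not replace them.

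Three further inferences are tempting and unsupported:

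- *That the protocol expects scattered single symptoms.* Item 10 is a risk disclosure and predicts no pattern. The drug background in Section II expects no side effects at or below therapeutic serum levels.
- *That the trigger of three is to blame.* Step 1 shows that it costs no by-term significance.
- *That the report would declare no difference.* Nothing says so. Events are summarised by group, and the principal investigator reviews them after each subject (item 12), so untested does not mean unseen. Neither provision, however, supplies a pre-specified comparison between groups.

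**Conclusion.** The gap is real but conditional. The plan has no participant-level safety comparison. If affected participants report about one symptom each, spread over the 13 listed, a test is the exception up to 10 of 15 affected in a group. Detection is then about 10% against about 57% pooled, under assumed rates of 40/10/10. The advantage narrows with two symptoms each at 10% background, and reverses with three, or with two or three at 20% background. All rates, symptom counts and weights are assumptions. The change is worth making because it is cheap and the population is healthy. It does not invalidate the planned safety analysis.

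**What to change.** In the safety paragraph of item 13:

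1. Add one pre-specified comparison: the participant had at least one toxicity symptom listed in item 10 during dosing. Make it among the three groups whether or not the trigger is met. Report rate differences with exact confidence intervals. An exact test is preferable at 15 per group.
2. Fix the symptom list in the analysis plan. Item 10's toxicity list is open-ended, and nausea, vomiting, diarrhea and loss of appetite also appear under allergic reaction. Define what counts as a specific event by coding or grouping terms.
3. Keep the by-term summary and the planned by-term tests, labelled exploratory because they are uncorrected.
4. State that participants removed under the stopping criteria in item 4 stay in this comparison. That item excludes their data from the analysis without saying whether safety is exempt.
5. Reconcile 45 (3 × 15) with 60 subjects, since this sets the denominator.

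The cost is wording and one derived variable from data already collected. The downsides are small: one more test adds slightly to false alarms, and the pooled endpoint weights mild and serious symptoms equally and takes in nonspecific ones. The by-term table guards against the last two.
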